This study is funded by the National Institute for Health Research (NIHR) Health Technology Assessment (NIHR130580). The views expressed are those of the author(s) and not necessarily those of the NIHR or the Department of Health and Social Care.

This protocol is for prediction modelling (work package 2) of the grant:

The development of risk-stratified, cost-effective, and acceptable blood-test monitoring strategies for inflammatory conditions treated with commonly used immune suppressing drugs: a multi-method study using evidence synthesis, modelling and qualitative research (NIHR130580).

Please see below for a description of the other work-packages

Question: What is the optimum strategy of blood testing after the first 6 month of immune-suppressing drug prescription?

Objectives: [1] Investigate association between different strategies of testing and target-organ damage detection. [2] Identify prognostic factors associated with target-organ damage. [3] Develop a prediction model for target-organ damage conditional on the prognostic factors. [4] Evaluate cost-effectiveness of risk-stratified testing strategies. [5] Assess patients' and clinicians' views and experiences of current testing strategies, and the acceptability of recommended strategies.

Methods: The study will be delivered in 3 interlinked work packages (WPs) with patient and public input throughout.

WP 1 (Evidence synthesis): Delivers objectives 1-2. A conventional (Review 1) and prognostic (Review 2) systematic review will be performed adhering to the York CRD guidance and PROGRESS framework respectively. Cochrane Risk of Bias, ROBINS-I and QUIPS checklists will be used for quality assessment as appropriate. Data on patient characteristics, monitoring strategies, adverse events, drug discontinuations (Review 1); and prognostic factors for developing adverse events (Review 2) will be extracted. Evidence will be assessed using the GRADE and meta-analysed using random effects model if appropriate.

WP 2 (Prediction, health economic modelling): Delivers objectives 3-4. Routine healthcare data from Clinical Practice Research Datalink (CPRD) Gold and Aurum will be used to develop and validate a prognostic model. CPRD is an anonymized, longitudinal database of UK primary-care records established in 1987. It provides data on demographics, lifestyle factors, diagnoses, blood test results, and GP prescriptions. Data on prognostic factors identified in WP1 (Review 2) will be extracted from the CPRD and used to develop a risk-score

using a penalized flexible parametric survival model. Risk thresholds to be used in the health economic models will be agreed using decision curve analysis and with patient and clinician involvement. After this, a mathematical model will be formed to compute cost-effectiveness of frequency of testing at different levels of risk. The model will be in line with the NICE reference case using a lifetime horizon and estimating a cost per QALY gained for alternative frequency of testing strategies. The uncertainty of results will be explored with confidence intervals, cost-effectiveness planes and cost-effectiveness acceptability curves.

WP 3 (Qualitative): Delivers objective 5. Patients and healthcare professionals will be recruited to explore their views on current and recommended monitoring strategies. Both purposive stratified and maximum variation sampling will be employed to include patients with different diseases, treatments, and at varying risk of adverse-events. Semi-structured interviews will be conducted using interview topic guide created with PPI input. Data will be transcribed verbatim, anonymised, and analysed using inductive thematic analysis.

Study title: The development of risk-stratified blood-test monitoring strategies for common inflammatory conditions treated with immune suppressing drugs

Section 1: General Information

Research area Drug Safety, Pharmacoepidemiology *Does this protocol describe an observational study using purely CPRD data?* Yes

Additional information from GPs and contact with patients

Does this protocol involve requesting any additional information from GPs, or contact with patients? No

Section 2: Research team Applicant's role

Role: Corresponding applicant

Email: [contact] Name: [name] Statistical experience: Yes Experience of handling large datasets: Yes Experience of practicing in UK primary care: No Will the applicant be analysing the data? Yes

Chief investigator

Do you require data linkages? Yes - I do require data linkages Patient level data HES Admitted Patient Care

Area level data Do you require area level data? **No**

Withheld concepts Are withheld concepts required? No

Linkage to a dataset not listed Are you requesting a linkage to a dataset not listed? No

Patient data privacy

Does any person named in this application already have access to any of these data in a patient identifiable form, or associated with an identifiable patient index? **No**

Section 5. Protocol information

Lay summary

Medicines such as methotrexate suppress the immune-system and are used to treat conditions like rheumatoid arthritis (RA) that result from an overactive immune-system. Patients treated with these medicines may develop side-effects such as blood, liver or kidney damage, and, fortnightly to monthly blood tests are performed to detect them early, before any permanent damage can occur. However, these side-effects become less common after the first few months of treatment. Nevertheless, monitoring with periodic blood tests is continued indefinitely for all patients treated with these medicines. The benefit from such long-term monitoring is not known, and, whether all patients should undergo regular blood-tests indefinitely needs to be determined.

We want to find out the best strategy for long-term monitoring of people with inflammatory conditions (e.g. RA, psoriasis, inflammatory bowel disease etc.) treated with immune-suppressing medicines, specifically, methotrexate, sulfasalazine, aminosalicylates (e.g. mesalazine), azathioprine, and mycophenolate.

For this, we will use anonymized information from a healthcare database (Clinical Practice Research Datalink), which includes information on the treatment and monitoring of adults registered with a large number of general practices in the UK. We will use information about risk factors such as age, sex, body mass index, other illnesses, lifestyle factors (such as alcohol intake, smoking) and prescription of other medicines to develop a score to calculate the risk of blood, liver, or kidney damage over a 5-year time-period for people treated with these medicines. A separate risk score will be calculated for each medicine of interest named in the previous paragraph.

Technical summary

Background: The optimal monitoring strategy for adults with common inflammatory conditions treated with long-term immune-suppressing drugs is not known.

Question: What is the optimum strategy of blood testing after the first six months of primary-care immune-suppressing drug prescription?

Objectives: [1] Develop and validate a prediction model for estimating an individual's risk of target-organ damage conditional on their values of multiple prognostic factors available at 6 months of primary-care immune-suppressing drug prescription, [2] Identify incidence of drug discontinuation for any reason, and due to abnormal monitoring blood test results in each year of prescription.

Methods: Data from Clinical Practice Research Datalink (CPRD) Gold and Aurum will be used. We will utilise CPRD-HES linked data to validate the sensitivity of outcome definition in primary-care data alone.

People with common inflammatory conditions treated with immune-suppressing drugs, will be followed up electronically from day 180 of the first primary-care prescription of a drug of interest until the earliest of target-organ adverse event, drug discontinuation, death, moving to a different practice, 5-year follow-up time, or 31/12/2019 (study end date).

A penalized flexible parametric survival model will be used to develop a risk prediction score for drug discontinuation due to target organ damage using CPRD Aurum given its larger sample size, accounting for competing risks as necessary, and with internal validation using bootstrapping to quantify and adjust for optimism. The predictive performance of the score will be validated in CPRD Gold. GP practices contributing data to both CPRD Aurum and GOLD will be excluded from the validation cohort. Separate risk scores will be developed and validated for each drug of interest. Risk thresholds will be agreed using decision curve analysis and with patient and clinician involvement. Incidence (per 1,000 person-years) of treatment discontinuation in each 12-month of primary-care prescription will be estimated.

Outcomes to be measured

Primary outcome: Drug discontinuation due to target organ specific adverse event. This will be defined as drug discontinuation with either (a) abnormal blood test results due to target-organ damage, or (b) target organ damage based on clinical code allocation.

Drug discontinuation due to abnormal monitoring blood test results will be defined as present when there is:

(a) a gap between two prescriptions, or between the last prescription date and earliest of death date, moving to a different practice, 5-year follow-up time, or 31/12/2019 (study end date) of \geq 90 days, and

(b) the last prescription is preceded in up to 15 days by abnormal blood test results (to account for any delay in acting on abnormal results) or followed by an abnormal test result in the next 45 days.

Abnormal blood test results will be defined according to the British Society for Rheumatology DMARD monitoring guidelines1, and CKD progression will be defined as per the Kidney Disease Improving Global Outcomes guideline 20122:

- White blood cells <3.5x109/L,
- Neutrophils <1.6x109/L,
- Platelets <140x109/L,
- Alanine Transaminase and/or Aspartate Transaminase >100 units/L,

• CKD progression defined as creatinine difference > 26 micro mol/L above the first or second preceding blood-test result or chronic kidney disease stage progression.

In addition to the above blood-test abnormalities, in people with psoriasis, methotrexate discontinuation will be defined to be due to blood-test abnormalities if (i) serum amino-terminal pro-peptide of type III procollagen (PIIINP) is > 8 mg/L on two previous occasions; (ii) if three previous PIIINP measurements were >4.2 mg/L in the previous 12-month period; or (iii) if previous PIIINP measurement was > 10 mg/L as per guidelines for the British Association of Dermatologists [3].

Secondary outcome: Drug discontinuation due to any reason.

Defined as present if there is a gap between two prescriptions, or between last prescription date and earliest of death date, moving to a different practice, 5-year follow-up time, or 31/12/2019 (study end date) of ≥ 90 days.

Objectives, specific aims and rationale

The overall purpose of this study is to ascertain the optimum strategy of blood testing for adults with common inflammatory conditions treated with immune-suppressing drugs after the first six months of primary-care prescription. By strategy we mean the optimum frequency of testing, and how the frequency of testing should alter according to the individual's risk.

The objectives are to:

[1] Develop and validate a prediction model estimating an individual's risk of target-organ damage conditional on their values of multiple prognostic factors available at six months of immune-suppressing drug prescription.

[2] Identify incidence of drug discontinuation due to any reason and due to abnormal monitoring blood test results in each year of prescription.

Synergy with ongoing research: We have an ISAC approved study (reference number 19_275R) developing a risk-prediction score for liver, blood or kidney damage from methotrexate and leflunomide in people with auto-immune rheumatic diseases, using data from the Clinical Practice Research Datalink (CPRD).

We are seeking approval for additional work to [1] conduct prediction modelling for azathioprine, sulfasalazine, aminosalicylates (such as mesalazine), and mycophenolate, and [2] expand analysis of methotrexate to include patients with psoriasis (without psoriatic arthritis) and inflammatory bowel disease.

Leflunomide is only licenced for the treatment of RA and psoriatic arthritis and we do not propose to expand the modelling to other common inflammatory conditions for this drug for this reasons.

We can confirm that these analyses were not included in our previously approved application.

Study background

A. What is the problem being addressed?

Rheumatoid arthritis, inflammatory bowel disease, psoriasis +/- arthritis, ankylosing spondylitis and systemic lupus erythematosus affect 1 in 30 adults in the UK, and are treated with immune suppressing drugs such as methotrexate, azathioprine and sulfasalazine etc. [4-9]. These medicines can cause symptomatic side-effects such as nausea, vomiting, headache, infections etc., and asymptomatic side-effects such as acute liver or kidney injury, or low blood cell count. Clinical experience and research studies identified in our scoping review suggest that both symptomatic and asymptomatic side-effects generally occur within the first six months of starting treatment [10-14], and, because of this increased risk of drug toxicity, treatment is initiated in a hospital clinic with dose escalation guided by disease activity, and fortnightly-to-monthly tests of full blood count, renal and liver function performed to detect any asymptomatic abnormalities early. Unless there are early side-effects and the treatment is stopped, most patients achieve their target dose between three to four months of starting treatment. Just after this, the responsibility for prescribing and monitoring, including with three-monthly blood tests is handed-over to the patients' general practitioner (GP). The intended purpose of such monitoring is to facilitate early detection of an abnormality, allowing the offending treatment to be stopped before any permanent damage occurs. However, there is scant evidence that long-term use of these immune suppressing medicines causes blood, liver, or kidney damage [10-14]. Thus, this strategy for long-term monitoring with periodic blood tests for all patients appears to be based on convention, inertia, and perceived safety, rather than on a robust evidence base.

Moreover, the recommendations for monitoring differ across specialties. For example, the British Association of Dermatology recommends measuring serum amino-terminal propeptide of type III procollagen (PIIINP), a biomarker of liver fibrosis for methotrexate prescriptions, while the British Society for Gastroenterology and British Society for Rheumatology do not recommend such testing [1,15,16]. Such inconsistencies cause confusion, and may result in excessive monitoring or in monitoring not being done. Similarly, while the summary of product characteristics and clinical guidelines recommend more frequent haematological and biochemical monitoring in individuals with comorbidities, such as excess alcohol use, extremes of body mass index (e.g. <18 or >35 kg/m2), old age and renal impairment, the way in which these factors interact with drugs to produce target organ damage such as low blood count, or kidney or liver injury varies across studies, and, has not been systematically reviewed [17-22]. A risk prediction model incorporating these factors has not been developed, and the optimum monitoring strategy in terms of frequency, and the tests to include is not known.

How does the existing literature support this proposal?

There is no published systematic review of the evidence for long-term blood-monitoring. A review just on methotrexate toxicity is ongoing since 2013 (CRD42015020254) according to a search of PROSPERO on 29/07/2019. Our scoping review suggests that monitoring tests are rarely abnormal after the first year of treatment. In clinical trials, fewer than 2% of people prescribed methotrexate and none prescribed leflunomide discontinued treatment

due to blood test abnormalities after the first year (n=1,198) [10, 23, 24]. Similar findings were observed in other observational studies of leflunomide and methotrexate treatment [11,25]. Thus, the greatest utility of these monitoring blood tests appears to be in the first year of treatment, with the risk reducing with increasing treatment duration.

Although renal function testing is included in regular monitoring for methotrexate, low-dose methotrexate, as used in the treatment of autoimmune inflammatory diseases has a low rate of acute kidney injury e.g. 1.9/1000 person-years in a nationwide Danish study (mean follow-up period 4 years), with three-quarter of such events occurring within the first eight months of treatment [26]. In keeping with the above, >98% of liver and bone marrow adverse events due to azathioprine occurs within the first year of treatment as observed in previous systematic reviews [12,27]. Similarly, a cohort study of 739 people with inflammatory bowel disease followed-up for up to 11 years, reported only two cases of clinically severe leukopenia (less than $2000/\mu$ L) after the first 12 month of treatment [13]. Many of the drug discontinuations reported in these older studies would not occur in clinical practice nowadays as these were relatively early clinical trials, and the current threshold for drug discontinuation due to abnormal blood-test results e.g. alanine transferase (ALT) more than 3 times the upper limit of normal, are significantly higher than those used in these studies e.g. ALT more than 1.2-1.4 times the upper limit of normal [28]. Generally, druginduced liver injury occurs within the first few months of drug initiation. For instance, in one study, the median (inter-quartile range) time between first drug prescription and liver injury, defined as liver enzyme levels >5 times normal was only 42 (20–117) days, and 5.5% of the 254 liver injuries were due to immune-suppressing drugs [14]. There are no data demonstrating that routine periodic blood test monitoring after a year of treatment is effective in preventing serious adverse drug reactions, compared to symptom-driven testing [29]. Additionally, small observational studies suggest that cumulative dosing of medicines such as methotrexate does not correlate with toxicity [30-33]. Our limited review suggests that most blood, liver, and kidney-related adverse events occur within first few months of treatment, and only a small proportion of drug discontinuations occur due to these after the first year. Ongoing regular monitoring can be onerous for patients, incurs costs, and false positive results prompt unnecessary testing and treatment. There is variability in guidance across disciplines. Hence, there is need for a study to determine optimal monitoring strategy.

We propose to use existing data from routine treatment of people with inflammatory diseases prescribed selected immune-suppressing drugs in the UK to develop risk prediction models.

Study type Pharmacoepidemiology study, drug-safety study.

Study design Prospective cohort study.

Feasibility counts According to a feasibility count using data from 731 GP practices (n=3,023,253 adults contributing to CPRD Gold) in the year 2018, there were over 40,000 participants in receipt of at-least one primary-care prescription for the drugs of interest.

Please see Table 1 for individual drugs. As we will utilise data from 2007-2019, we anticipate greater number of participants. For instance, in our ongoing study (ISAC reference number 19_275R), 24,871 people in CPRD Gold dataset were prescribed methotrexate between the years 2007 and 2019 of which 15,670 incident users were included in the analyses after applying the inclusion and exclusion criteria. Among these participants, there were 1,262 methotrexate discontinuations for acute kidney, liver or bone-marrow toxicity. Of the discontinuations due to abnormal blood test results, a random sample of 505 cases demonstrated that 95% discontinuations could not potentially be explained by another underlying illness, its treatment, or complication recorded in the CPRD.

Sample size considerations

Proportion discontinuing drugs due to abnormal blood-test results:

Based on data from our ongoing study, there are 15,670 people with auto-immune rheumatic diseases prescribed methotrexate of which 8% discontinued methotrexate due to blood-test result abnormalities. Assuming a similar discontinuation rate for all inflammatory conditions, we should be able to estimate the same proportion with a margin error based on 99% confidence interval of +/- 0.55%. Values for other drugs in Table 1 should be estimated with similar or greater precision as the source population (Aurum) will be larger.

Risk prediction model:

Sample size for prediction modelling should aim to minimise overfitting and estimate key parameters precisely. This is the premise of Riley et al [34] sample size criteria. Assuming a mean follow-up of 1 year and a rate of 0.02 per person year such that at 6 months outcome risk is 1%, then the max R squared is 0.18. Conservatively assuming that 15% of variation is explained by our model (model R squared is 0.027), then with 50 candidate predictor parameters, the criteria of Riley et al [34] suggests 6.57 events per parameter, therefore 329 outcome events are required, and 16,416 participants are needed for developing the prognostic model.

We will use data from CPRD Aurum to develop the prognostic model for mesalazine, sulfasalazine, azathioprine, and mycophenolate. We are reasonably confident that there will be sufficient sample size to develop a prognostic model for all drugs of interest with the exception of mycophenolate.

Our ongoing ISAC approved study (ISAC reference number 19_275R) has used data from CPRD Gold to develop a prognostic model for methotrexate toxicity in patients with autoimmune rheumatic diseases, and is validating it using data from the CPRD Aurum. To maintain synchrony with ongoing research we will include data for patients with psoriasis and inflammatory bowel diseases treated with methotrexate in CPRD Gold database in the model development dataset and from CPRD Aurum database when validating prognostic model for methotrexate toxicity.

Planned use of linked data and/or withheld concepts HES admitted patient care:

We anticipate that serious blood, liver or renal organ system drug toxicities may lead to hospitalisation and these outcome events may not be ascertained using primary care

dataset alone if the abnormal blood-test result is not recorded in primary care. However, our clinical experience suggests that such outcomes are very rare. Due to sample size limitations (as 68.5% and 65.7% of CPRD Gold and Aurum respectively have linkage to HES), an analysis restricted to CPRD-HES linked data is not appropriate, as a third of sample-size will be lost with only a few outcome events gained. Therefore, a sample will be drawn from the study population with HES linkages to validate the sensitivity of outcome definition using primary-care data alone.

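### The prediction-model sample size is correct for its inputs, but 1 year of mean follow-up and a 2% event fraction match neither the 5-year score nor the 8% reported for methotrexate

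*Protocol*

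**What the plan says.** Under Sample size considerations (Risk prediction model), the protocol sets out its inputs: "Assuming a mean follow-up of 1 year and a rate of 0.02 per person year such that at 6 months outcome risk is 1" per cent. From this it states: "then the max R squared is 0.18". It takes 15% of that maximum (0.027) as the model R-squared, allows 50 candidate parameters, and concludes: "therefore 329 outcome events are required, and 16,416 participants are needed for developing the prognostic model".

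The Lay summary says that the team will "develop a score to calculate the risk of blood, liver, or kidney damage over a 5-year time-period". Cohort exit is capped at 5 years, and the primary outcome runs from month 6 to year 5 after the first primary-care prescription.

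Feasibility counts reports, for 15,670 incident methotrexate users in the ongoing study: "Among these participants, there were 1,262 methotrexate discontinuations for acute kidney, liver or bone-marrow toxicity". The first part of Sample size considerations rounds this to 8% and carries it across inflammatory conditions to work out the precision of the discontinuation proportion.

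**The concern.** Two calculations under one heading use event fractions four-fold apart, 8% and 2%, with no reason given. One year of mean follow-up is also unexplained beside a 5-year horizon. The maximum R-squared depends on the event rate and mean follow-up. So, through the 15% rule, do the model R-squared, the number of people needed and the events per parameter. The figure of 6.57 therefore does not carry over to a cohort with longer follow-up or more events.

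The plan's own methotrexate cohort shows the difficulty. Its 15,670 people fall just short of the 16,416 needed, while its 1,262 events are 3.8 times the 329 required (1,262 / 329 = 3.84). A separate model is planned for each drug. For a smaller cohort the two printed figures can point in opposite directions, and the protocol does not say which one governs.

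**Working it through.** **Inputs from the protocol:** rate 0.02 per person-year; mean follow-up F = 1 year; P = 50 parameters; R-squared = 15% of its maximum; 1,262 events in 15,670 people.

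**Assumed, because the protocol does not state them:** target shrinkage S = 0.9, and mean follow-up in the real cohorts, varied from 1 to 4.5 years. The upper end is the longest possible time at risk between month 6 and year 5.

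**Formulas** (the sample-size criteria that the protocol cites, time-to-event form):
- Event fraction E = rate × F
- Maximum R-squared = 1 − exp(2 × E × (ln(rate) − 1))
- People n = P / ((S − 1) × ln(1 − R-squared / S))
- Events = n × E

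**Step 1: the plan's own figure.** E = 0.02 × 1 = 0.02. Maximum R-squared = 1 − exp(0.04 × (ln 0.02 − 1)) = 0.178, printed as 0.18. R-squared = 0.15 × 0.18 = 0.027. n = 50 / (−0.1 × ln(1 − 0.03)) = 16,416. Events = 16,416 × 0.02 = 328.3, printed as 329. Per parameter, 328.3 / 50 = 6.57. All printed figures reproduce.

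**Step 2: the plan's own data.** 1,262 / 15,670 = 8.05%, which is 4.03 times 2%. At 0.02 per person-year, that fraction takes about 4 years of mean follow-up.

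**Step 3: 8% event fraction, 15% rule kept.**

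| Mean follow-up | Rate | Max R-squared | People | Events | Events per parameter |
|---|---|---|---|---|---|
| 1 y | 0.08 | 0.431 | 6,706 | 536 | 10.7 |
| 2 y | 0.04 | 0.491 | 5,859 | 469 | 9.4 |
| 3 y | 0.0267 | 0.523 | 5,485 | 439 | 8.8 |
| 4 y | 0.02 | 0.544 | 5,258 | 421 | 8.4 |
| 4.5 y | 0.0178 | 0.553 | 5,173 | 414 | 8.3 |

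The printed 16,416 is 2.4 to 3.2 times these numbers of people. The printed 329 is 21% to 39% below these numbers of events.

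**Step 4: rate kept at 0.02, follow-up lengthened.** This does not use the 8% figure.

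| Mean follow-up | People | Events |
|---|---|---|
| 2 y | 8,980 | 359 |
| 3 y | 6,483 | 389 |
| 4 y | 5,258 | 421 |

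**Step 5: 329 events alone, at 8%.** 329 / 0.08 is about 4,113 people. Solving the formula for n as an equation in S gives expected shrinkage of 0.847 (1 y), 0.864 (2 y), 0.876 (4 y) and 0.878 (4.5 y), against the target of 0.90.

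**Step 6: both printed figures together, at 8%.** 16,416 people would give 16,416 × 0.08 = 1,313 events and expected shrinkage of about 0.96.

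**Step 7: the 6-month time point.** It does not enter the formula for n. Moving it to 5 years leaves 16,416 and 329 unchanged.

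**Step 8: lower rates.** At 0.01 per person-year over 3 years (E = 3%), maximum R-squared is 0.286 and the need is 10,253 people and 308 events. At 0.005 over 3 years (E = 1.5%), it is 0.172, with 17,174 people and 258 events.

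**The case against.** The strongest reply is that the printed pair is safe. The protocol asks for 329 events and 16,416 people together, and a cohort meeting both reaches expected shrinkage of about 0.90 or better across the event fractions tried. That stands. The event figure is too low only when it is read alone and the event fraction is well above 2%.

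The 8% is also documented only for methotrexate in autoimmune rheumatic disease. The protocol extends it across conditions, not expressly across drugs, and does not say whether it counts events before day 180. Its background cites fewer than 2% of methotrexate users in trials stopping for abnormal tests after year one. This too stands: 8% is a scenario, not the right value for every drug, and step 8 shows that the event shortfall disappears at low rates.

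The opposite movement of the two figures depends on the 15% rule. If R-squared is held at 0.027, n stays at 16,416 and the matching events at 8% are 1,313. The 15% rule is the plan's own, however, so recomputing the maximum is the natural reading.

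Two stronger inferences are tempting and should not be drawn:
- **That 16,416 is a go/no-go threshold.** No section says so. The protocol speaks only of reasonable confidence for most drugs and possible failure for mycophenolate. It keeps methotrexate, which is below 16,416, on the strength of its events.
- **That 16,416 is why the analysis is not run on linked hospital data.** That section does begin "Due to sample size limitations (as 68.5% and 65.7% of CPRD Gold and Aurum respectively have linkage to HES". Its argument, though, is that a third of the sample would be lost for few extra events, and the option is reopened if sensitivity proves low.

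Finally, the study uses all existing data, and the analysis section applies bootstrap optimism correction and uniform shrinkage. This limits the damage from a modest shortfall, but it does not make the stated sample size match the design.

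**Conclusion.** The point holds as a mismatch of inputs, not an arithmetic error. One year of mean follow-up and a 2% event fraction do not describe a 5-year score, and they sit beside an 8% fraction from the team's own cohort.

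Under the plan's own rules the participant figure is overstated and the event figure, read alone, is understated. This is true in every scenario with 8% events (1 to 4.5 years) and in those with 0.02 per person-year over 2 to 4 years. It rests on S = 0.9, on keeping the 15% rule, and on a mean follow-up that the protocol does not give. For drugs with event fractions at or below about 2%, the direction can differ.

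The methotrexate model is not threatened: 15,670 people and 1,262 events exceed every recalculated requirement. The table of per-drug counts is not in the text available, so no drug is shown to be misjudged. The consequence is limited to how the less-used drugs are assessed, but the correction is cheap and worth making.

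**What to change.** Recalculate the risk-prediction part of Sample size considerations for the 5-year horizon. Use the event rate and mean follow-up observed in the ongoing methotrexate cohort after day 180, with a range of lower rates for the other drugs, and state the shrinkage target.

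Replace the single pair of 329 events and 16,416 people, and the 6.57 events per parameter, with the resulting scenario table. Say that each drug will be judged on expected shrinkage at its own number of people and event fraction, with fewer candidate parameters where it falls below 0.9. The figures for 8% events given here are scenario values and should not be written in for every drug.

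The cost is a short recalculation from figures that the team should already hold, plus a wording change; no new data are needed. The downside is that the required number of events may become less favourable for some drugs, so that a small cohort has to enter fewer predictors.
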